#### **5.5.2.1 Prohibited Concomitant Medications for Preladenant**

Specific restrictions for preladenant administration (Arm 1 and Arm 2) during the course of the trial are listed. These are based on the current known metabolism of the drugs as described. Restrictions may be removed if indicated by emergent data from drug-drug interaction trials. Any medications/therapies no longer contraindicated will be communicated

to the site by an administrative letter. The following medications/therapies are not permitted from 2 weeks prior to Day 1 through 2 weeks after the study treatment period.

For subjects who, in the assessment of the investigator, require the use of any of the aforementioned treatments for clinical management should be discontinued. Subjects may receive other medications that the investigator deems to be medically necessary.

- Inhibitors/inducers/substrates of CYP3A4 and substrates for CYP2C8 enzymes.

Preladenant is a competitive and irreversible metabolism-dependent inhibitor of cytochrome P450 (CYP) 3A4, a substrate of CYP3A4, and a direct competitive inhibitor of CYP2C8. As such, concomitant use of other drugs that are identified in [Table 11](#) as strong inducers, strong or moderate inhibitors, or substrates (characterized with a narrow therapeutic range) of CYP3A4 or CYP2C8, is prohibited while the subject is enrolled in this study.

If the use of a CYP3A4 or CYP2C8 medication listed in [Table 11](#) is medically necessary, and an alternate therapeutic agent is not available, then the subject must discontinue treatment with preladenant.

Preladenant may potentially inhibit the activity of other CYP3A4 or CYP2C8 substrates that are not identified as prohibited in [Table 11](#). Caution and close drug monitoring is strongly advised when preladenant is administered concomitantly with other CYP3A4 or CYP2C8 substrates. See [Table 11](#) for more detailed information regarding adverse effects of CYP3A4 substrates with a narrow therapeutic range.

Investigators should check an actively updated list of drugs that are clinically relevant substrates, inducers or inhibitors of cytochrome P450, including CYP3A4 (<http://medicine.iupui.edu/clinpharm/ddis/table.asp>) as well as the product labeling of these compounds for reference.

CYP3A4 inhibitors/inducers/substrates are listed below. The subject must not take the treatments listed in [Table 11](#) during the trial after the start of the study treatment. Since this list is not comprehensive, the investigator should use his/her medical judgment when a subject presents with a medication not on the list or call the Sponsor Clinical Director for clarification.

Table 11 Medications, Supplements, and Other Substances Prohibited During the Trial

Strong 3A4 Inducers a,d	Strong CYP3A4 Inhibitors b,d	Moderate CYP3A4 Inhibitors b,d	CYP3A4 or CYP2C8 Substrates With Narrow Therapeutic Range c,d	Other
carbamazepine phenobarbital phenytoin rifabutin rifampin troglitazone	indinavir nelfinavir ritonavir clarithromycin itraconazole ketoconazole nefazodone atazanavir saquinavir telithromycin cannabis (oral; IV)	amprenavir aprepitant diltiazem erythromycin fluconazole fosamprenavir verapamil grapefruit, starfruit juices	alfentanil c ergotamine c diergotamine c cyclosporine c fentanyl c pimozide c quinidine c sirolimus c tacrolimus c astemizole c,e terfenadine c,e cisapride c,e paclitaxel c repaglinide c lurasidone c	Any chemotherapy Any biologic therapy Any hormonal therapy Investigational drugs Radiation therapy (except palliative radiation to isolated lesions after discussion with the Sponsor) Proton-pump inhibitors

CYP = cytochrome P450.
 
a Strong 3A4 inducers listed are those that decrease plasma AUC values of 3A4 substrates by 30% or higher.
 
b Moderate inhibitors are defined as causing a <math>\geq 2</math>- but <math>< 5</math>-fold increase in the AUC values or 50-80% decrease in clearance of sensitive CYP3A substrates when the inhibitors were given at the highest approved dose and the shortest dosing interval in clinical evaluations. Strong inhibitors are defined as causing a <math>> 5</math>-fold increase in the plasma AUC values or more than 80% decrease in clearance.
 
c CYP3A4 and CYP2C8 substrates with narrow therapeutic range refers to drugs whose exposure-response indicates that increases in their exposure levels by the concomitant use of CYP3A4 or CYP2C8 inhibitors may lead to serious safety concerns. For specific information, see the Classification of Substrates tables available at: http://www.fda.gov/Drugs/DevelopmentApprovalProcess/DevelopmentResources/DrugInteractionsLabeling/ (then click "Drug Development and Drug Interactions: Table of Substrates, Inhibitors and Inducers")
 
d Compiled from the in vivo inhibitors and inducers, inhibitor classification, and substrate classification tables available at: http://www.fda.gov/Drugs/DevelopmentApprovalProcess/DevelopmentResources/DrugInteractionsLabeling/ (then click "Drug Development and Drug Interactions: Table of Substrates, Inhibitors and Inducers") and from the CYP450 drug interaction table (accessed June 2012) available at: http://medicine.iupui.edu/clinpharm/DDIs/table.aspx.
 
e Not available in the United States, and limited availability in the European Union.
				

- Proton-pump inhibitors

The subject must not take proton-pump inhibitors (PPI) during the trial from 5 days before the start of the study treatment to 5 days following the last administration of preladenant. The investigator should use his/her medical judgment when a subject presents with a PPI treatment or call the Sponsor Clinical Director for clarification.

Of note, antacids, such as calcium carbonate or aluminum hydroxide-based product, will be allowed during the study, and are recommended to be taken either 4 hours before or after dosing of preladenant.

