### **5.5.2.2 Prohibited Concomitant Medications for Pembrolizumab**

Systemic glucocorticoids > 10 mg for any purpose other than to modulate symptoms from an adverse event are not allowed. However, the use of physiologic doses of corticosteroids may be approved after consultation with the Sponsor:

- Inhaled steroids as part of a stable regimen for the treatment of asthma/chronic obstructive pulmonary disease [COPD] are permitted.
- Use of physiologic doses of corticosteroids ( $\leq 10$  mg daily of prednisone equivalent) as replacement therapy for endocrinopathies may be approved after consultation with the Sponsor.
- Non-immune suppressing doses of steroids in patients with stable CNS metastases may be approved after consultation with the Sponsor.
- Additionally, a short limited course of steroids may be used to treat medical conditions and/or adverse events during the study after sponsor notification and consultation.
- Use of prophylactic corticosteroids to avoid allergic reactions (e.g. IV contrast dye) is permitted.
- Use of non-systemic steroids is permitted.

Section 5.1.3 Subject Exclusion Criteria describes other medications that are prohibited in this trial.

There are no prohibited therapies during the Post-Treatment Follow-up Phase.

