#### **7.1.1.6.2 Concomitant Medications**

The investigator or qualified designee will record medication, if any, taken by the subject during the trial through the Post-Treatment Safety Follow-Up visit, 30 days after the last dose of study drug.

After the Safety Follow-Up visit, all medications related to reportable SAEs and ECIs as defined in Section 7.2, should be recorded.

All new anti-cancer therapy initiated after the study start must be recorded in the eCRF. If a subject initiates another anti-cancer therapy other than the assigned study treatment(s), the study treatment(s) should be discontinued and the subject will move into the survival follow-up phase; if a subject initiates a new anti-cancer therapy within 30 days after the last dose of the trial treatment, the 30 day Safety Follow-up visit should occur before the first dose of the new therapy.

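### For subjects who receive both drugs, Sections 5.5.2.1 and 5.5.2.2 give conflicting rules on which therapies are barred after treatment ends

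*Combined protocol and SAP*

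**What the plan says.** Section 5.5.2.1 sets restrictions for preladenant in Arms 1 and 2. Its lead-in reads: "The following medications/therapies are not permitted from 2 weeks prior to Day 1 through 2 weeks after the study treatment period". The reason given is metabolic: "Preladenant is a competitive and irreversible metabolism-dependent inhibitor of cytochrome P450 (CYP) 3A4", and the drug also inhibits CYP2C8 competitively. Table 11 lists strong CYP3A4 inducers, strong and moderate CYP3A4 inhibitors, and narrow-range CYP3A4 or CYP2C8 substrates, among them paclitaxel, fentanyl, cyclosporine and tacrolimus. Its last column adds chemotherapy, biologic and hormonal therapy of any kind, and proton-pump inhibitors (PPIs). A footnote says that raised exposure to the narrow-range substrates "may lead to serious safety concerns".

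Section 5.5.2.1 then gives further periods. One sentence bars the CYP-interacting drugs for as long as the subject is enrolled. Another bars everything in Table 11 during the trial once treatment has started. PPIs have their own rule: "from 5 days before the start of the study treatment to 5 days following the last administration of preladenant".

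Section 5.5.2.2 is headed "Prohibited Concomitant Medications for Pembrolizumab". It closes with: "There are no prohibited therapies during the Post-Treatment Follow-up Phase". The sentence names a trial phase and no drug.

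**The concern.** A site caring for a subject who has just stopped combination treatment needs to know whether a Table 11 agent may be started, and from when. Section 5.5.2.1 says it may not be started yet; the last sentence of 5.5.2.2 says nothing is off limits. A site relying on 5.5.2.2 could start a drug that 5.5.2.1 bars, in a class for which the protocol itself records a safety concern.

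Two things are at stake. The first is subject safety during the period that 5.5.2.1 protects. The second is interpretation: adverse events from an interaction with the next therapy would be tabulated against the preladenant dose level, and sites and monitors could not agree on whether the early start was a protocol deviation.

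**Working it through.** There is no statistical figure to reproduce. The check sets the texts side by side.

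| Source | What it covers | Bar after treatment |
|---|---|---|
| 5.5.2.1, lead-in | Listed therapies, Arms 1 and 2 | 14 days from the end of the study treatment period |
| 5.5.2.1, CYP paragraph | Strong inducers, strong or moderate inhibitors, narrow-range substrates | As long as the subject is enrolled |
| 5.5.2.1, sentence before Table 11 | All of Table 11 | During the trial; no end point given |
| 5.5.2.1, PPI bullet | PPIs | 5 days from the last preladenant dose |
| 5.5.2.2, closing sentence | All therapies, as worded | None (0 days) |

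**Who is under both sections.** Section 8.9 plans 26 subjects in Part 1 Arm 2 and 60 in Part 2: 26 + 60 = 86 of 112, or 77%. Arm 1 subjects who cross over come on top; their number is not given. This counts subjects governed by both rules. It does not count subjects harmed, or subjects who start a listed drug early.

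**When the rules collide.** Section 5.8.1 keeps subjects in the trial after they stop treatment, so the enrolment-based bar runs on through follow-up and conflicts with 5.5.2.2 throughout. The 14-day bar conflicts with 5.5.2.2 on any of Days 1 to 14 after the study treatment period that count as post-treatment follow-up. The text does not define when that phase begins. In the flow chart its first visit is 30 days after the last dose. But 7.1.1.6.2 provides that, "if a subject initiates a new anti-cancer therapy within 30 days after the last dose of the trial treatment", this visit comes before the first dose of the new therapy, so it can fall within the first 14 days.

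**Where the 14 days start.** The lead-in counts from the end of the study treatment period, while the PPI bullet counts from the last preladenant dose. Section 2.1 allows pembrolizumab to continue alone in Arm 2 after preladenant is stopped. If it continues for D days, the lead-in bar ends D + 14 days after the last preladenant dose. One further 21-day cycle, taken as an illustration, gives 21 + 14 = 35 days instead of 14.

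**Whether other text settles it.** It does not.
- Section 5.5.2 limits its general list to screening and treatment.
- Section 2.1 leaves treatment after discontinuation to the physician.
- Section 5.5.2.1 requires preladenant to stop if a listed CYP drug is unavoidable, but gives no interval before that drug starts.
- Sections 7.1.1.6.2 and 7.1.5.3.2 foresee new anticancer therapy within 30 days and refer to neither rule.

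**Where a toxicity would be counted.** A subject who starts new anticancer therapy before day 30 is still followed for adverse events to day 30 (7.1.5.3.2). If Days 1 to 14 are counted from treatment discontinuation, a start in that span leaves between 30 − 14 = 16 and 30 − 1 = 29 days of collection. Such events enter the summaries by dose level and arm in 8.6.2. The primary endpoint is the DLT rate, observed on Days 1 to 21 of Cycle 1 (5.2.2), so it is largely untouched.

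**The case against.** The best defence is the heading. Sections 5.5.2.1 and 5.5.2.2 can be read as parallel drug-specific lists, so that the closing sentence of 5.5.2.2 lifts only the pembrolizumab restrictions and the preladenant bar stands for anyone who took preladenant. That reading is fair. It means a reader should not infer that the protocol plainly permits paclitaxel the day after treatment stops: 5.5.2.1 still forbids it. It also disposes of Arm 1 unless the sentence is taken as trial-wide. It does not remove the problem. The sentence follows a trial-wide reference to the exclusion criteria, it is framed by phase and not by drug, and sites are left to infer an interaction rule.

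Other inferences are tempting but unsupported:
- **Sections 7.1.1.6.2 and 7.1.5.3.2 authorise an early start.** They fix visit and adverse-event timing. A start on days 15 to 29 after treatment ends can satisfy both them and the 2-week bar.
- **PPI entry rules conflict.** Exclusion 7 and the PPI bullet both say 5 days; only the general 2-week lead-in blurs this.
- **Nearly every subject is affected, above all in triple-negative breast cancer.** No rate of early next-line therapy is given, and that tumour type is only an example for Part 2.
- **CYP3A4 inhibition outlasts the drug by a known time.** The documents call it irreversible and give no recovery time.

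**Conclusion.** The contradiction is real and sits in current text. For subjects who receive both drugs, the post-treatment bar on a Table 11 CYP drug is 0 days, 14 days or the whole time enrolled, depending on the sentence followed. The starting point of the 14 days is also unsettled when pembrolizumab continues alone. About 86 planned subjects, plus cross-overs, are governed by both sections; the number who would meet the conflict in practice cannot be derived.

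The clash with the 14-day bar rests on two assumptions: that the closing sentence of 5.5.2.2 is taken as worded, and that post-treatment follow-up can begin within 14 days of the end of treatment. The clash with the enrolment-based bar needs only the first.

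This is a safety-wording defect that should be corrected. A reader might infer that it undermines the primary endpoint or the dose decisions. The documents do not support that, because DLTs are confined to Cycle 1. Sample size and error rates are not involved.

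**What to change.** The sponsor should reconcile Section 5.5.2.1, Table 11 and the closing sentence of 5.5.2.2 so that subjects who took preladenant have one post-treatment rule. That rule needs one starting point, either the end of the study treatment period or the last preladenant dose, and the text should say when post-treatment follow-up begins. Sections 7.1.1.6.2 and 7.1.5.3.2 should refer to it, since they foresee new anticancer therapy within 30 days. As a minor tidy-up, say that the 2-week lead-in does not apply to PPIs, if the 5-day text is meant to govern.

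Which interval stands is for the sponsor to decide; this review takes no position. The cost is protocol wording at the next amendment. The small downside is that the timing of some subjects' next therapy may have to be checked against the reconciled rule.

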### **5.5.2.2 Prohibited Concomitant Medications for Pembrolizumab**

Systemic glucocorticoids > 10 mg for any purpose other than to modulate symptoms from an adverse event are not allowed. However, the use of physiologic doses of corticosteroids may be approved after consultation with the Sponsor:

- Inhaled steroids as part of a stable regimen for the treatment of asthma/chronic obstructive pulmonary disease [COPD] are permitted.
- Use of physiologic doses of corticosteroids ( $\leq 10$  mg daily of prednisone equivalent) as replacement therapy for endocrinopathies may be approved after consultation with the Sponsor.
- Non-immune suppressing doses of steroids in patients with stable CNS metastases may be approved after consultation with the Sponsor.
- Additionally, a short limited course of steroids may be used to treat medical conditions and/or adverse events during the study after sponsor notification and consultation.
- Use of prophylactic corticosteroids to avoid allergic reactions (e.g. IV contrast dye) is permitted.
- Use of non-systemic steroids is permitted.

Section 5.1.3 Subject Exclusion Criteria describes other medications that are prohibited in this trial.

There are no prohibited therapies during the Post-Treatment Follow-up Phase.

## **5.6 Rescue Medications & Supportive Care**

### **5.6.1 Supportive Care Guidelines for Preladenant**

Medications required to treat AEs or concurrent illnesses other than those prohibited in [Table 11](#) are allowed during the study. Contraceptive medications as described in Section 5.1 are allowed.

Bisphosphonates are allowed for subjects with lytic bone metastases.

Antiemetics, including serotonin-receptor antagonists, metoclopramide, prochlorperazine, or thiethylperazine are allowed. Aprepitant is a CYP3A4 inhibitor and should not be used in the study.

Asymptomatic increases in liver enzymes have been noted in human subjects receiving preladenant. Liver function will be monitored throughout the clinical study as recommended by the FDA Guidance for Industry Drug-Induced Liver Injury: Premarketing Clinical Evaluation [21].

Administration of preladenant to healthy volunteers and subjects with Parkinson's disease have been associated with transient non-dose-related increases in systolic and diastolic BP. Blood Pressure monitoring will be conducted during the clinical study as appropriate to further evaluate these changes and to support subject safety. Acute and symptomatic rises in BP should be treated according to the standard of care.

Every medication taken by the subject during the trial and the reason for use must be recorded in the eCRF. Note that the use of any concomitant medication must relate to the documented medical history, prophylaxis, or an adverse event of the subject. Subjects will be permitted to receive appropriate supportive care measures as deemed necessary by the treating physician.

Please refer to preladenant investigator brochure (IB) for detailed information.

### **5.6.2 Supportive Care Guidelines for Pembrolizumab**

Subjects should receive appropriate supportive care measures as deemed necessary by the treating investigator. Suggested supportive care measures for the management of adverse events with potential immunologic etiology are outlined along with the dose modification guidelines in Section 5.2.3.2, [Table 8](#). Where appropriate, these guidelines include the use of oral or intravenous treatment with corticosteroids, as well as additional anti-inflammatory agents if symptoms do not improve with administration of corticosteroids. Note that several courses of steroid tapering may be necessary as symptoms may worsen when the steroid dose is decreased. For each disorder, attempts should be made to rule out other causes such as metastatic disease or bacterial or viral infection, which might require additional supportive care. The treatment guidelines are intended to be applied when the investigator determines the events to be related to pembrolizumab.

Note: If after the evaluation the event, it is determined not to be related, the Investigator does not need to follow the treatment guidance. Refer to [Table 8](#), Section 5.2.3.2 for guidelines regarding dose modification and supportive care.

It may be necessary to perform conditional procedures such as bronchoscopy, endoscopy, or skin photography as part of evaluation of the event.

Please refer to pembrolizumab IB for detailed information.

## **5.7 Diet/Activity/Other Considerations**

### **5.7.1 Diet**

Foods that are CYP3A inhibitors must not be consumed during the study. Grapefruit and star fruit are known to be CYP3A inhibitors, and should not be consumed for 2 weeks before the first dose of preladenant and for the entire duration of the study. Consumption of CYP3A4 inhibitors, such as grapefruit juice, may significantly increase the levels of preladenant and cause increased toxicity. St. John's Wort is a CYP3A inducer, and the consumption of St. John's Wort or products containing St. John's Wort may reduce the levels of preladenant. A partial list of CYP3A inhibitors is provided in Section 5.5.2.1.

### 5.7.2 Contraception

Preladenant and/or pembrolizumab may have adverse effects on a fetus in utero. Furthermore, it is not known if preladenant and/or pembrolizumab have transient adverse effects on the composition of sperm.

For this trial, male subjects will be considered to be of non-reproductive potential if they have azoospermia (whether due to having had a vasectomy or due to an underlying medical condition).

Female subjects will be considered of non-reproductive potential if they are either:

- postmenopausal (defined as at least 12 months with no menses without an alternative medical cause; in women < 45 years of age a high follicle stimulating hormone (FSH) level in the postmenopausal range may be used to confirm a post-menopausal state in women not using hormonal contraception or hormonal replacement therapy. In the absence of 12 months of amenorrhea, a single FSH measurement is insufficient.);

OR

- have had a hysterectomy and/or bilateral oophorectomy, bilateral salpingectomy or bilateral tubal ligation/occlusion, at least 6 weeks prior to screening;

OR

- has a congenital or acquired condition that prevents childbearing.

Female and male subjects of reproductive potential must agree to avoid becoming pregnant or impregnating a partner, respectively, while receiving study treatment and for 120 days after the last dose. Subjects must comply with one of the following:

- practice abstinence from heterosexual activity.

Abstinence (relative to heterosexual activity) can be used as the sole method of contraception if it is consistently employed as the subject's preferred and usual lifestyle and if considered acceptable by local regulatory agencies and European Research Councils (ERCs)/Institutional Review Boards (IRBs). Periodic abstinence (e.g., calendar, ovulation, symptothermal, post-ovulation methods, etc.) and withdrawal are not acceptable methods of contraception.

OR

- use (or have their partner use) acceptable contraception during heterosexual activity.

Acceptable methods of contraception are‡:

- Single method (one of the following is acceptable):
  - intrauterine device (IUD)
  - vasectomy of a female subject's male partner
  - contraceptive rod implanted into the skin

- Combination method (requires use of two of the following):
  - diaphragm with spermicide (cannot be used in conjunction with cervical cap/spermicide)
  - cervical cap with spermicide (nulliparous women only)
  - contraceptive sponge (nulliparous women only)
  - male condom or female condom (cannot be used together)
  - hormonal contraceptive: oral contraceptive pill (estrogen/progestin pill or progestin-only pill), contraceptive skin patch, vaginal contraceptive ring, or subcutaneous contraceptive injection

‡If a contraceptive method listed above is restricted by local regulations/guidelines, then it does not qualify as an acceptable method of contraception for subjects participating at sites in this country/region.

Subjects should be informed that taking the study medication may involve unknown risks to the fetus (unborn baby) if pregnancy were to occur during the study. In order to participate in the study, subjects of childbearing potential must adhere to the contraception requirement (described above) from the day of study medication initiation (or 14 days prior to the initiation of study medication for oral contraception) throughout the study period up through 120 days after the last dose of trial medication. If there is any question that a subject of childbearing potential will not reliably comply with the requirements for contraception, that subject should not be entered into the study.

